3.4.7 Replacement of Subjects

Part 1 and Part 2

Any subject who does not complete Cycle 2 may be replaced at the discretion of the study investigator and sponsor. Should the decision be made to replace a subject, the replacement subject will be assigned to the same treatment combination regimen as the original subject.

Part 3

Any subject who does not complete study therapy through Cycle 1 for reasons other than the occurrence of a DLT may be replaced at the discretion of the study investigator and sponsor. Should the decision be made to replace a subject, the replacement

subject will be assigned to the same treatment combination regimen as the original subject.

3.4.8 Enrollment and Procedures

Part 1

Enrollment of a subject into the study will be performed according to the following procedure:

- The study center will notify the sponsor when a clinically eligible subject is identified and is ready to screen, to ensure enrollment availability on the study.
- After the subject has signed and dated the Informed Consent Form (ICF), all screening procedures have been completed, and eligibility has been confirmed, the subject can be officially enrolled in the study.
- To enroll a subject and confirm eligibility, the study center will fax/email a completed Enrollment Confirmation Form to the sponsor. The enrollment date will be the date that the form is faxed/emailed to the sponsor.
- An Enrollment Confirmation Form will be completed and faxed/emailed to the study center by the sponsor within 24 hours.
- The Enrollment Confirmation Form will contain treatment allocation generated by the sponsor.
- The sponsor will aim to fax/email a completed Enrollment Confirmation Form to the study center within 24 hours of receipt.

Treatment must begin within the screening window (Section 4.1) and after the site has received the treatment allocation from the sponsor. Study treatment is not blinded on this study.

Part 2 and Part 3

Subjects will be enrolled in Part 2 and Part 3 according to the following procedure:

- The Sponsor's clinical team will inform all sites which part of the study is open for enrollment.
- The study center will notify and obtain an approval of the histology from the sponsor when a potential subject is identified and ready to be screened.
- After the subject has signed and dated the ICF, all screening procedures have been completed, and eligibility has been confirmed, the subject can be officially enrolled in the study.

 To enroll a subject and confirm eligibility, the study center will fax/email a completed Enrollment Confirmation Form to the sponsor. The enrollment date will be the date that the form is faxed/emailed to the sponsor.

 The sponsor will aim to fax/email a signed and completed Enrollment Confirmation Form to the study center within 24 hours of receipt.

Study treatment must begin within the screening window (Section 4.1).

3.5 STUDY DRUG

3.5.1 Premedications

No specific premedications or supporting medications are required in conjunction with acalabrutinib administration.

Prior to each rituximab infusion, subjects should be premedicated according to the Rituxan/MabThera package insert and institutional standard practices (e.g., with acetaminophen and an antihistamine). The Rituxan package insert warns that "Rituxan administration can result in serious, including fatal infusion reactions. Deaths within 24 hours of Rituxan infusion have occurred. Approximately 80% of fatal infusion reactions occurred in association with the first infusion. Monitor patients closely. Discontinue Rituxan infusion for severe reactions and provide medical treatment for Grade 3 or 4 infusion reactions."

Subjects receiving lenalidomide are at risk for venous and arterial thromboembolism and should receive low-dose aspirin as prophylaxis. Subjects at high risk for venous and arterial thromboembolism should receive additional prophylaxis including low molecular weight heparin, per the discretion of the investigator. High-risk subjects are those with a family history of venous thromboembolism, smoker, oral contraceptives, history of diabetes mellitus or coronary artery disease, and signs and symptoms of thromboembolism.

AEs of tumor lysis syndrome (TLS) have been observed in subjects treated with lenalidomide. Subjects at risk for TLS should be given TLS prophylaxis per institutional standard of care.

3.5.2 Formulation, Packaging, and Storage

Acalabrutinib is manufactured according to cGMP regulations and will be provided to the investigational site by the Sponsor or designee. Acalabrutinib should be stored according to the instructions on the label that is affixed to the package containing the drug product.

As of Clinical Study Protocol (CSP) Version 8.0, acalabrutinib is supplied in 2 formulations (hard gelatin capsules or orange film-coated tablets) for oral administration. Acalabrutinib capsules and tablets are bioequivalent. Each acalabrutinib capsule or tablet contains 100 mg of drug substance and standard pharmaceutical grade excipients. Acalabrutinib will be provided in white, high-density polyethylene bottles.

If a drug shipment arrives damaged, or if there are any other drug complaints, a Product Complaint Form should be completed and emailed or faxed to the Sponsor or the Sponsor's representative.

Refer to the Acalabrutinib Investigator Brochure for additional information.

Rituximab (Rituxan/MabThera) injection is a commercial product (Genentech, Inc., South San Francisco, CA/Roche, Basal Switzerland). Rituximab is available in 100 mg/10 mL single-use vials and 500 mg/50 mL single-use vials.

Lenalidomide (Revlimid[®]) is a commercial product (Celgene, Inc, Summit, NJ). Lenalidomide is available as capsules containing 2.5 mg, 5 mg, 10 mg, 15 mg, 20 mg, and 25 mg of drug substance.

Refer to product information from the manufacturers for details on formulation, packaging, and storage of rituximab and lenalidomide.

3.5.3 Administration of Study Drug

Investigators are prohibited from supplying acalabrutinib to any subjects not properly enrolled in this study. The investigator must ensure that subjects receive acalabrutinib only from personnel who fully understand the procedures for administering the drug.

Acalabrutinib is intended to be administered orally with 8 ounces (approximately 240 mL) of water. Acalabrutinib taken with an acidic beverage may impact exposure to acalabrutinib (refer to the current Acalabrutinib Investigator brochure). Acalabrutinib may be administered without regard to food. The capsules or tablets should be swallowed intact and subjects should not attempt to open capsules or crush tablets, and both formulations should not be dissolved in water.

Acalabrutinib should be taken BID, approximately 12 hours apart. Dietary restrictions are provided in Section 3.7.4.

If a dose is missed, it can be taken within 3 hours after the scheduled time with a return to the normal schedule with the following dose. If the time from the scheduled time of

administration has been >3 hours, the dose should not be taken, and the subject should take the next dose. The missed dose will not be made up and must be returned to the site at the next scheduled visit.

Rituximab is to be administered as an IV infusion, not an IV push or bolus. Detailed instructions for the preparation and administration of rituximab are provided in the Rituxan/MabThera package insert and per institutional standards. No dose reductions for rituximab are allowed. On days when both acalabrutinib and rituximab are administered, the rituximab infusion should begin approximately 1 hour after the acalabrutinib dose.

Subjects will continue on acalabratinib after completion of rituximab treatment or may do so if rituximab is discontinued due to intolerability at any time in the study.

Lenalidomide is to be administered orally at approximately the same time each day, either with or without food. The capsules should be swallowed whole with water. The capsules should not be opened, broken, or chewed. Lenalidomide is administered for the first 21 days of each 28-day cycle. On days that both acalabrutinib and lenalidomide are administered, lenalidomide should be taken approximately 30 minutes prior to the first daily dose of acalabrutinib. Dose modification provisions are provided in Section 3.5.7.

3.5.4 Assuring Subject Compliance

Subjects will receive their supply of acalabrutinib in the clinic on Day 1 of Cycle 1 and Cycle 2, and Day 1 of subsequent scheduled visits. For treatments that are taken in the clinic, subjects should take acalabrutinib from the drug dispensed for them for that particular time period. All other acalabrutinib treatments will be taken at home. Subjects will receive a diary to record the specific time each dose was taken and to record reasons for any missed doses.

Subject compliance will be assessed at every visit. The subject will be instructed to bring the diary and any remaining capsules or tablets to the clinic at their next visit. The administrator will review the diary and ask the subject if all the capsules or tablets were administered. Any remaining or returned capsules and tablets will be counted and recorded as described in Section 7.11. Returned capsules and tablets must not be redispensed to another subject. The study staff will resupply the subject with the correct number of capsules or tablets needed for use until the next visit.

3.5.5 Definition of Dose-limiting Toxicity (Part 3)

A DLT will be defined as the occurrence of any of the following study drug-related AEs

during the DLT review period. (Note: AEs clearly related to disease progression or the subject's medical history and associated comorbidities considered by the investigator to be unrelated to study drugs, will not be considered DLTs. Infusion reactions clearly associated with rituximab infusion will not be considered DLTs.):

- 1. Non-hematologic DLTs include:
 - a) Grades 3 or 4 nausea, vomiting, or diarrhea lasting >7 days despite optimal antiemetic or antidiarrhea management or any Grade 3 or Grade 4 toxicity
 - b) Any grade Stevens-Johnson syndrome or toxic epidermal necrolysis
 - c) AST or ALT >3 × ULN concurrently with total bilirubin >2 × ULN
 - d) Clinical TLS not resolving to baseline after a 2-week treatment delay
- Exceptions are deep vein thrombosis (DVT), correctable electrolyte
 abnormalities, or Grade 3 or Grade 4 laboratory abnormalities lasting ≤7 days;
 Grades 3 or 4 fatigue, anorexia, non-neutropenic fever, Grade 3 rash resolving to
 Grade 2 within 10 days (allowed therapy with steroids)
- 2. Hematologic DLTs include:
 - a) Grade 3 or Grade 4 neutropenia with fever ≥38.5°C or infection, or Grade 4 neutropenia lasting >7 days despite adequate granulocyte-colony stimulating factors (G-CSF) use
 - b) Grade 3 or Grade 4 thrombocytopenia with hemorrhage. If thrombocytopenia improves to Grade ≤2 or to ≥80% of the baseline value within 28 days, without a platelet transfusion, this will not be considered a DLT
 - c) Any Grade 4 hematologic toxicity unrelated to the underlying disease
- 3. Any study drug-related Grade 5 AE
- 4. Any study drug-related toxicity leading to an individual drug dose delay of >21 consecutive days for acalabrutinib or >14 consecutive days for lenalidomide will be considered as a DLT. Subjects should receive at least one dose of rituximab in Cycle 1 to be evaluable for a DLT.

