- b. The starting dose of lenalidomide is 15 mg QD and the final dose for the expansion portion of the study will be determined based on the outcome of the DLT review. Subjects will receive lenalidomide at the assigned dose or the final dose for up to 12 cycles or until disease progression or intolerance, whichever comes first.

Acalabrutinib has been used in combination with rituximab at the doses mentioned above and this combination has an acceptable safety profile (current version of Acalabrutinib Investigator Brochure). There will be an inter-subject dose escalation or de-escalation during the DLT review period to find the appropriate dose of lenalidomide that can be used in combination with acalabrutinib and rituximab.

DLT review and enrollment are presented in Figure 3 and will be conducted as follows (DLT criteria are defined in Section 3.5.5):

Expand cohort Lenalidomide 20 mg QD Rolling DLT < 2/6 DLT *Inter-subject Dose Escalation for subjects N = 14without toxicity review Lenalidomide Rolling DLT 20 mg QD review < 2/6 DLT *N=6 ≥ 2 DLT Expand cohort Lenalidomide Lenalidomide 15 15 mg QD mg QD *N=6 N=14 Rolling DLT Expand cohort review Lenalidomide 10 mg QD < 2/6 DLT N=14 ≥ 2 DLT Lenalidomide 10 mg QD N=6 **Acalabrutinib dose will not be reduced unless specific toxicity ≥2DLT clearly attributable to acalabrutinib occurs. No dose reduction for STOP rituximab per label

Figure 3 Dose-Limiting Toxicity Review and Enrollment for Part 3

 $\label{eq:decomposition} \mbox{DLT=dose-limiting toxicity; QD=once per day}.$

Six subjects are planned to be enrolled initially and treated with acalabrutinib, rituximab, and lenalidomide (15 mg PO QD) in Cycle 1. At the end of the cycle, subjects will be evaluated for DLTs on a rolling basis (Figure 3).

- If there are ≥2 subjects with DLTs on 15 mg of lenalidomide QD, the dose of lenalidomide will be reduced to 10 mg QD, and 6 more subjects are planned to be enrolled at this reduced dose of lenalidomide.
 - If there are ≥2 subjects with DLTs at the end of Cycle 1 on 10 mg lenalidomide QD, enrollment will close.
 - If there are <2 of 6 subjects with DLTs, then approximately 14 additional subjects will be enrolled and treated with lenalidomide 10 mg QD for Cycles 1 through 12.
- If there are <2 of 6 subjects with DLTs on 15 mg QD, 6 additional subjects are planned to be enrolled to receive an increased dose of lenalidomide at 20 mg QD.

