 - If there are ≥2 subjects with DLTs, the dose of lenalidomide will be reduced back to 15 mg QD. Approximately 14 more subjects will be added to complete enrollment at the 15-mg QD dose.
 - If there are <2 of 6 subjects with DLTs, 20 mg of lenalidomide will be the dose used for Cycles 2 through 12. Approximately 14 more subjects will be added to complete enrollment.

Note: Subjects will be evaluated for DLTs at the end of the first cycle, on a rolling basis, when they complete a cycle of treatment.

Refer to Appendix 6 for a comprehensive list of study assessments and their timing.

Part 4

At the time of Amendment 6, the sponsor made the decision to close Part 4 cohort to enrollment. Therefore, Part 4 has been removed.

All Parts

Twenty-eight days of study drug administration is 1 cycle. Treatment with acalabrutinib may be continued until confirmed disease progression or an unacceptable drug-related toxicity occurs.

Dose modification provisions are provided in Section 3.5.7. Note: Temporary withholding of acalabrutinib for as little as 7 days can cause a transient worsening of disease and/or of constitutional symptoms. All subjects who discontinue study drug

will have a safety follow-up visit 30 (+7) days after the last dose of study drug until the final data cut-off regardless of whether the subject receives a new anticancer therapy or demonstrates disease progression within this timeframe.

All subjects will have hematology, serum chemistry, hepatitis serology, and urinalysis safety panels performed at screening. For Part 1 and Part 2, once dosing commences (Day 1), all subjects will be evaluated for safety, including hematology and serum chemistry, once weekly for the first 4 weeks, every 2 weeks in Cycle 2, monthly through Cycle 13, and then every 3 months thereafter. For Part 3, once dosing commences (Day 1), all subjects will be evaluated for safety, including hematology and serum chemistry, once weekly for the first 4 weeks, every 2 weeks in Cycle 2, and monthly through Cycle 13, and for Part 3, every 8 weeks starting Cycle 14 up to Cycle 28 (rituximab infusion ends at Cycle 26) and every 3 months thereafter.

Part 3

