3.5.7 Dose Modification and Discontinuation

All acalabrutinib dose modifications (Table 1 and Table 2) should be discussed with the medical monitor prior to instituting changes. For toxicities that are common to both acalabrutinib and lenalidomide, consider adjusting the dose of lenalidomide before adjusting the dose of acalabrutinib per the recommendations below:

- Grade 4 neutrophil count decreases (ANC <500/µL) for >7 days (hematopoietic colony-stimulating factors are permitted per American Society of Clinical Oncology [ASCO] guidelines] and use must be recorded on the electronic case report form [eCRF])
- Grade 3 platelet count decreases in the presence of significant bleeding
- Grade 4 platelet count decreases
- Grade 3 or 4 nausea, vomiting, or diarrhea, if persistent despite optimal antiemetic and/or antidiarrheal therapy
- Any other Grade 4 toxicity or unmanageable Grade 3 toxicity

Table 1 Drug Modification and Discontinuation Actions for Acalabrutinib (in Combination with Lenalidomide)

Occurrence	Action
1st–2nd	Hold acalabrutinib until recovery to Grade ≤2 or baseline; may restart at
100 2110	original dose level (100 mg BID)
3rd	Hold acalabrutinib until recovery to Grade ≤2 or baseline; restart at 100 mg
ord	once daily
4th	Discontinue acalabrutinib

BID=twice daily.

Table 2 Drug Modification and Discontinuation Actions for Acalabrutinib (Without

Lenalidomide)

Action
Hold acalabrutinib until recovery to Grade ≤1 or baseline; may restart at
original dose level (100 mg BID)
Hold acalabrutinib until recovery to Grade ≤1 or baseline; restart at 100 mg
once daily
Discontinue acalabrutinib

BID=twice daily.

Whenever possible, any dose adjustment of acalabrutinib should be discussed between the investigator and the Sponsor's medical monitor before implementation. The appropriate clinic staff should dispense the study drug for the new dose level and instruct the subject/caregiver about the change in dose level. Any changes to the dosing regimen must be recorded on the appropriate eCRF.

Rituximab dose modifications should follow the recommendations in the Rituxan/MabThera package insert and institutional standard practices.

Per the lenalidomide label, the dose adjustments listed in Table 3 are acceptable for lenalidomide.

Table 3 Dose Modification Actions for Lenalidomide

Toxicity	Dose Adjustment
Platelets <50 × 10 ⁹ /L:	Interrupt and follow CBC weekly

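### Part 3 DLT items 2b and 2c conflict: a drug-related Grade 4 thrombocytopenia with hemorrhage that recovers untransfused is excluded by one and counted by the other, with no rule on which prevails

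*Protocol*

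**What the plan says.** Protocol Section 3.5.5 opens by making a DLT the occurrence of any listed study drug-related event in the review period. Two of its hematologic items concern platelets.

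- Item 2b names Grade 3 or 4 thrombocytopenia with hemorrhage. It then adds a recovery sentence: if thrombocytopenia improves to Grade 2 or below, or to at least 80% of baseline, "within 28 days, without a platelet transfusion, this will not be considered a DLT".
- Item 2c is "Any Grade 4 hematologic toxicity unrelated to the underlying disease". It has no bleeding, duration or recovery condition.

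The synopsis repeats both items. The list of exceptions in 3.5.5 belongs to the non-hematologic item and does not bear on this.

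The DLT count drives Section 3.1. At the starting dose, "If there are ≥2 subjects with DLTs on 15 mg of lenalidomide QD" leads to 10 mg, and fewer than 2 of 6 opens 20 mg. At 20 mg, two or more mean "the dose of lenalidomide will be reduced back to 15 mg QD", with about 14 expansion subjects at that dose; fewer than two mean about 14 at 20 mg. At 10 mg, two or more close enrollment.

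Section 3.5.5 also sets an evaluability condition: "Subjects should receive at least one dose of rituximab in Cycle 1 to be evaluable for a DLT". SAP Sections 5.1 to 5.3 define all-treated, efficacy-evaluable and PK populations only, and SAP Section 7.7 lists no DLT summary.

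**The concern.** A dose-finding rule needs each event to have one classification. Here one type of event has two, and the protocol does not say which applies. The threshold is two subjects out of six, so one classification can decide whether the dose goes up, goes down, or sets the expansion level. At 20 mg it decides which dose about 14 further subjects receive.

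Classification also touches cohort membership. Section 3.4.7 reads: "Any subject who does not complete study therapy through Cycle 1 for reasons other than the occurrence of a DLT may be replaced". The choice lies with the investigator and the sponsor. A subject who stopped early with a disputed event would count against the dose under 2c, but could be replaced under 2b.

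Safety is the primary objective of Part 3. Without a planned DLT count by dose level, a reader of the report may not be able to tell which reading supported the chosen dose.

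**Working it through.** The documents state no operating characteristic for the 2-of-6 rule, so there is no figure of the plan's own to reproduce on this point. The check is mainly textual.

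**Step 1: classify each type of event.** Take a drug-related thrombocytopenia that recovers as 2b describes, within 28 days and untransfused.

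| Event | 2b, exclusion limited to bleeding events | 2b, exclusion covering all thrombocytopenia | 2c | Conflict? |
|---|---|---|---|---|
| Grade 3, bleeding | excluded | excluded | not met | none |
| Grade 4, bleeding | excluded | excluded | counted | on both readings |
| Grade 4, not bleeding | not addressed | excluded | counted | on the wider reading only |

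The width of the conflict depends on what *this* refers to in the recovery sentence. The bleeding Grade 4 row conflicts either way.

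**Step 2: look for a tie-breaker.** Nothing in 3.5.5 ranks 2b against 2c. Section 3.5.7 lists "Grade 3 platelet count decreases in the presence of significant bleeding" and then, with no condition, "Grade 4 platelet count decreases". That pattern favors letting 2c govern Grade 4. But 3.5.7 is a dose-modification list, and 3.5.5 does not refer to it.

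**Step 3: effect of one event.** Cohort size is 6 and the switch is at 2 (Section 3.1).

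- One event changes the observed rate by 1/6 = 16.7 percentage points.
- 1 of 6 = 16.7%, exact (Clopper-Pearson) 95% interval 0.4% to 64.1%: below the switch.
- 2 of 6 = 33.3%, interval 4.3% to 77.7%: at the switch.

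The intervals overlap almost entirely, yet the rule gives opposite decisions.

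**Step 4: illustration with assumed rates only.** Let *p* be the undisputed DLT rate and *d* the rate of disputed events per subject. Neither is in the documents. Counting disputed events can only add DLTs, so

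P(the two readings disagree in one cohort) = P(X ≥ 2 | 6, p + d) − P(X ≥ 2 | 6, p).

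Example with p = 10%, d = 2%: 0.1556 − 0.1143 = 0.041.

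| p | d = 1% | d = 2% | d = 5% |
|---|---|---|---|
| 5% | 1.3% | 2.8% | 8.1% |
| 10% | 2.0% | 4.1% | 10.9% |
| 20% | 2.5% | 4.9% | 12.1% |

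If a cohort already has exactly one undisputed DLT, the chance is 1 − (1 − d/(1 − p))^5. For p = 10%, d = 2% this is 10.6%; over the same grid it runs from 5.2% to 27.6%. These figures show sensitivity to the wording. They do not estimate what happened in this trial.

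**The case against.** The strongest reply is that the documents, read sensibly, already give an answer. The recovery sentence sits inside 2b directly after thrombocytopenia with hemorrhage, so its natural subject is that event. A DLT is any listed item, so an event excused from 2b can still meet 2c, and 3.5.7 treats Grade 4 platelet falls without condition.

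The first part stands as a limit on scope. A reader might infer that every recovering Grade 4 thrombocytopenia is in conflict; the text does not establish that, because non-bleeding events may simply count under 2c. The second part does not remove the conflict. The sentence in 2b says the event is not a DLT at all, not merely that it fails 2b.

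Three further replies have force.

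- **Replacement.** Table 3 interrupts lenalidomide below 50 × 10⁹/L and resumes it 5 mg lower on recovery. A subject starting from 15 or 20 mg would therefore be expected to continue. DLT item 4 separately counts a related lenalidomide delay of more than 14 consecutive days. Replacement is discretionary. This consequence is possible but not prominent.
- **Frequency.** Part 3 entry requires platelets of at least 75 × 10⁹/L, and the Table 3 interruption also limits deep falls. The rates in step 4 are assumed.
- **The SAP.** A reader might infer that it drops a promised analysis. It does not. Protocol Section 3.1.2 and SAP Section 4.2 describe safety through adverse events and dose changes, and DLT is not a listed endpoint. Thrombocytopenia and hemorrhage tables and narratives are planned, and ad hoc analyses are allowed. The missing DLT set and table are a secondary reporting omission.

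**Conclusion.** The conflict between 2b and 2c is real and holds on either reading of 2b. For certain it covers drug-related Grade 4 thrombocytopenia with hemorrhage that recovers within 28 days without platelet transfusion. It covers non-bleeding Grade 4 events only if the 2b exclusion applies to all thrombocytopenia. One event is worth 16.7 percentage points in a cohort of six and can reverse a decision. Its frequency cannot be derived from the documents.

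SAP Section 7.5.3 gives the assigned lenalidomide dose as 15 or 20 mg, which suggests the step to 20 mg was already taken and the 10 mg branch not used. That is an inference, not a stated fact. If it is right, what remains at stake is mainly how dose selection is reported. A reader might also infer that the expansion dose was wrongly chosen. Nothing in the documents supports that: they contain no DLT results, and no disputed event is reported. Severity: minor to moderate.

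**What to change.** **Protocol 3.5.5 and synopsis.** Limit the recovery exclusion in 2b to Grade 3 thrombocytopenia with hemorrhage. All drug-related Grade 4 thrombocytopenia then counts under 2c, in line with the unconditional Grade 4 platelet bullet in 3.5.7. The alternative, restricting 2c to other Grade 4 hematologic toxicity, is less clean. It would also take Grade 4 neutropenia of 7 days or less out of 2c, and would leave unrecovered, non-bleeding Grade 4 thrombocytopenia unclassified.

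**Past decisions.** Do not reclassify them. If enrollment under the DLT rule is over, the wording change governs no new decision and serves to make the definition coherent.

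**Clinical study report, ideally planned in SAP Sections 5 and 7.7.**

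- Define DLT-evaluable subjects: at least one rituximab dose in Cycle 1, and either Cycle 1 completed or a DLT.
- Tabulate DLTs in that set per lenalidomide dose level used, listing replaced subjects with reasons.
- State which reading of 2b and 2c was applied, and whether any result of two or more in six differs under the other.

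**Cost.** A few words in two places, one population definition and one table, from adverse event, laboratory, dosing and concomitant-procedure data already collected. No extra patients or procedures. The downside is possible disclosure that a past dose decision depended on the reading.

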3.5.6 Dose Delays

Study treatment with acalabrutinib, rituximab, lenalidomide (if applicable), or combination treatment should be held for any unmanageable, potentially study drug-related toxicity that is Grade ≥3 in severity. Any other clinically important events where dose delays may be considered appropriate by the investigator must be discussed with the medical monitor. Study drug may be held for a maximum of 28 consecutive days from expected

dose due to toxicity. Study treatment should be discontinued in the event of a toxicity lasting >28 days, unless reviewed and approved by the medical monitor.

Note: Temporary withholding of acalabrutinib for as little as 7 days can cause a transient worsening of disease and/or of constitutional symptoms.

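### Part 3 takes the DLT count at the end of Cycle 1, before late-starting lenalidomide, acalabrutinib or TLS holds can meet the plan's own delay criteria, and nothing makes the 2-of-6 decision wait

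*Protocol*

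**What the plan says.** Protocol 3.5.5 counts drug-related events that occur "during the DLT review period" and gives that period no length in days. Two criteria depend on how long a hold lasts:

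- Item 4 covers a toxicity "leading to an individual drug dose delay of >21 consecutive days for acalabrutinib or >14 consecutive days for lenalidomide".
- Item 1d covers "Clinical TLS not resolving to baseline after a 2-week treatment delay".

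On timing, Section 3.1 states: "Subjects will be evaluated for DLTs at the end of the first cycle, on a rolling basis, when they complete a cycle of treatment". A cycle is 28 days. For the 10 mg branch, the same section ties the count explicitly to the end of Cycle 1. Fewer than two DLTs in six opens the next dose or the 14-subject expansion. Two or more lead to a lower dose or to closure. SAP 3.1 repeats the scheme, and SAP Section 5 defines no DLT-evaluable set.

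Holds can outlast the cycle. Section 3.5.6 says "Study drug may be held for a maximum of 28 consecutive days from expected" dose. Section 3.4.7 lets a Part 3 subject who does not complete Cycle 1 for reasons other than a DLT be replaced at discretion. The only evaluability condition in 3.5.5 is at least one Cycle 1 rituximab dose.

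**The concern.** A dose-clearance rule should not be able to fire before its own criteria can be met. Here the evaluation time is fixed by the cycle, while items 4 and 1d run on clocks that start with the hold. A hold that begins late in the cycle is neither a DLT nor a non-DLT when the count is taken. No text says how to score it, and the replacement rule could remove the subject from the six.

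Safety is the primary objective of Part 3. The 2-of-6 count decides whether six subjects go to 20 mg or about 14 enter expansion. With so few subjects, one open case can settle the decision.

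**Working it through.** **Plan's own figure.** The documents give no operating characteristic for the Part 3 rule, so there is none to reproduce.

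**Inputs.** Thresholds and items 1d, 2a-2c and 4: Protocol 3.5.5. Cycle of 28 days and lenalidomide on Days 1-21: Sections 3.1 and 3.5.3. Cycle 1 visits on Days 1, 8, 15 and 22, with ±2 days after Day 1, then Cycle 2 Day 1 (Day 29): Appendix 6.

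**Step 1: day count.** Calendar days, with the first held day counted as day 1. A hold starting on day d reaches its n-th day on day d + n - 1. The latest start classifiable by day T is T - n + 1.

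| Criterion | Days needed (n) | Latest start, T = 28 | Latest start, T = 29 |
|---|---|---|---|
| Lenalidomide, >14 | 15 | 14 | 15 |
| Acalabrutinib, >21 | 22 | 7 | 8 |
| TLS, 2 weeks | 14 | 15 | 16 |

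Cases still open on Day 29:

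- Lenalidomide holds from Days 16-21 reach the 15th day on 16 + 14 = 30 through 21 + 14 = 35.
- If the toxicity appears in the rest week (Days 22-28), the next expected lenalidomide dose is Day 29. The delay is classified on 29 + 14 = Day 43.
- An acalabrutinib hold from Day 9 reaches its 22nd day on 9 + 21 = Day 30. Later starts run later.
- TLS delays from Day 17 reach the 14th day on 17 + 13 = Day 30 or later.

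A lenalidomide hold from Day 15 is a boundary case. It has 28 - 15 + 1 = 14 days on Day 28, and Day 29 would be its 15th. Whether dosing resumes on Day 29 settles it.

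**Step 2: which events depend on these clocks.** Section 3.5.7 gives the Grade 4 level: "Grade 4 neutrophil count decreases (ANC <500" per µL). An ANC of 0.5-1.0 × 10⁹/L without fever or infection is therefore not a DLT under 2a or 2c, yet Table 3 interrupts lenalidomide once it has lasted 7 days. Platelets below 50 × 10⁹/L, short of Grade 4 and without hemorrhage, escape 2b and 2c, and Table 3's action is "Interrupt and follow CBC weekly". Such events can become DLTs only through item 4.

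The schedule produces open cases without unusual assumptions. Safety evaluation runs "including hematology and serum chemistry, once weekly for the first 4 weeks". An ANC below 1.0 first seen on Day 15 and confirmed on Day 22 falls in the rest week, which gives the Day 43 case. The ±2-day window can put the Day 15 visit on Day 16 or 17 and the Day 22 visit on Day 20 or 21. Unscheduled counts can also start a hold on Days 16-21.

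**Step 3: effect on the call, conditional.** Suppose one open subject is scored as no DLT and later proves to be one. The 2-of-6 call is wrong when exactly one of the other five has a DLT: P(X = 1) = 5p(1 - p)⁴.

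| Assumed DLT rate p | Probability that the call reverses |
|---|---|
| 0.10 | 0.328 |
| 0.20 | 0.410 |
| 0.33 | 0.333 |
| 0.40 | 0.259 |

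**The case against.** The strongest reply has five parts.

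**The Day 15 hold closes in time.** A reader might infer that the main failure is a lenalidomide hold from the Day 15 visit, one day short on Day 28. No visit is scheduled on Day 28. The next is Day 29, where that hold either reaches its 15th day or ends. This stands, and the point does not rest on that case.

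**The text allows two readings.** If a criterion must be met within Cycle 1, a late hold is not a DLT and nothing is mis-scored. If onset in Cycle 1 is enough, rolling review can add the DLT later. The documents compel neither. The first reading, however, makes a 15-day hold a DLT from Day 14 but not from Day 21, a distinction that no text states. Under the second, the dose may already be cleared when the DLT is added.

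**A held subject may not yet have completed a cycle of treatment.** On that reading the subject is still pending. The wording permits this but does not say it, and Section 3.4.7 points to replacement instead.

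**The sponsor would know.** Section 3.10 provides ongoing AE review and investigator calls covering AEs that lead to dose modification, and Section 3.4.8 has the sponsor confirm each enrollment. Open holds would probably be discussed. Neither section ties the dose decision to their resolution.

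**The reach is narrow and the decisions are probably made.** Both stand. Most non-hematologic Grade 3-4 events and all Grade 4 hematologic events unrelated to the disease are DLTs at onset. Section 3.5.7 permits colony-stimulating factors, and Table 3 resumes lenalidomide at ANC ≥1.0. SAP 7.5.3 lists assigned lenalidomide doses of 15 or 20 mg only.

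**Conclusion.** The point holds within limits. Applied as written, the end-of-cycle evaluation can clear a lenalidomide dose while an item 4 or item 1d case is still open. The open cases are lenalidomide holds from Days 16-21, Cycle 2 lenalidomide delays from a Cycle 1 toxicity, acalabrutinib holds from Day 9, and late TLS delays. The main clinical route is cytopenia short of Grade 4 without fever, infection or hemorrhage. This assumes calendar days, a review no later than about Day 29, and onset in Cycle 1 as the intended test.

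The only size given is conditional: a 26-41% chance that one mis-scored subject reverses the call, at assumed DLT rates of 10-40%. A reader might infer an overall inflation of the clearance probability. To get one, suppose up to 25% of true DLTs rest only on these clocks, and up to 2 of 6 of those are open under a 7-day entry stagger and a Day 29 review. The hidden share is then at most 0.25 × 2/6 = 0.083. The chance of fewer than two DLTs in six rises by at most 1.6 points at a 10% DLT rate, 4.1 at 20% and 5.7 at 33%, and by nothing at the low end. None of those inputs has a source in the documents, so no overall effect is claimed. Nor do the documents show that any subject was mis-scored or any dose wrongly cleared.

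**What to change.** Amend Protocol 3.1, 3.4.7 and 3.5.5 to say:

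- A DLT is a qualifying toxicity with onset in Cycle 1, followed until that criterion's own clock is complete.
- Item 4 counts calendar days. The SAP 7.5.3 withholding summary skips Days 22-28. On that convention a hold from Day 15 shows only 7 missed doses by Day 28.
- A subject on an unresolved toxicity hold is pending and may not be replaced.
- No escalation or expansion decision is made until all six subjects are classified or two DLTs have occurred.

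If the dose decisions have been taken, re-check every Cycle 1-onset hold in the DLT-review subjects from the dosing records that SAP 7.5.3 already uses. Report the corrected DLT count at each dose.

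The cost is wording, plus a wait only when a case is open. Past Day 28 the wait is at most about 15 days for lenalidomide (Day 43), 21 for acalabrutinib (start Day 28, Day 49) and 13 for TLS (start Day 28, Day 41).
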